## 11.2 Sample Size Considerations

This study plans to randomize 200 participants, which will provide 94% power (alpha = 0.05) to detect a difference between a 27% reduction in pain index in the propranolol arm and a 9% reduction in the placebo arm (primary hypothesis). Assuming haplotype distributions and within-haplotype treatment effects that are similar to those observed in the pilot study, the same sample size would provide 61% power (alpha = 0.05) to detect an interaction between haplotype and treatment group (secondary hypothesis). The assumptions for these power calculations are shown in the following table. Power calculations were made using the GLMPOWER procedure in SAS, which assumes a data structure of one observation per person. This is a simplification of the situation that will occur with the linear mixed model described in Section 11.4.1 in which efficacy will be evaluated using a data structure in which most participants will have three observations per person. The simplified power calculations are shown here because conventional software for power calculations does not deal with the more complex situation of linear mixed models.

		Primary Hypothesis		Secondary Hypothesis					
COMT haplotype		All haplotypes		0 LPS copies		1 LPS copy		2 LPS copies	
Treatment arm		Drug	Placebo	Drug	Placebo	Drug	Placebo	Drug	Placebo
% of participants (N = 200)		50%	50%	15%	15%	25%	25%	10%	10%
Mean baseline pain index		3000	3000	3000	3000	3000	3000	3000	3000
Net change		-810	-270	-1350	-270	-810	-270	-270	-270
Percentage change		-27	-9	-45	-9	-27	-9	-9	-9

\* LPS stands for low pain sensitive, one of the major haplotypes of *COMT*. The standard deviation for the mean baseline pain index is estimated to be 1190. The net change takes into account a 10% lost-to-follow-up rate and imputation using the last observation carried forward approach.

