### 11.4.1 Analysis of the Primary Hypothesis

The primary statistical analysis to evaluate the primary hypothesis will use all data from the intention-to-treat analytical sample in a linear mixed model. During the analysis of the primary hypothesis, treatment allocation will be masked (i.e., groups will be labeled A and B). Treatment allocation will be unmasked for further analyses.

---

The dependent variable will be the participant's change in the weekly pain index, computed as the weekly pain index at the follow-up visit (i.e., at Visit 2, Visit 3, or Visit 4) minus the Visit 1 weekly pain index. Explanatory variables will comprise fixed factors and a continuous covariate. The fixed factors will include the following: (a) treatment allocation (two categories) (b) visit sequence (three categories); (c) interaction of treatment allocation and visit sequence (two dummy variables); and (d) covariates of study site (three categories), sex (two categories) and race/ethnicity (probably three categories: non-Hispanic White, non-Hispanic Black, and other/multiple racial or ethnic groups – the final number of conditions will be dictated by the frequency distribution of race/ethnicity in the study sample). The baseline score collected at Visit 1 will be the continuous covariate, modeled as a fixed effect. The study participant will be modeled as a random factor.

In a linear mixed model containing all predictor variables including the interaction terms for visit and treatment allocation, the primary treatment effect will be tested at Visit 4. The null hypothesis of no treatment effect will be rejected if the P-value at Visit 4 is  $\leq 0.05$ . For descriptive purposes (and regardless of the P-value for efficacy at Visit 4), efficacy estimates at each visit (2, 3 and 4) will be described in terms of adjusted means and 95% confidence intervals.

If the propranolol treatment arm has a greater reduction in the weekly pain index than the placebo arm at Visit 4, a threshold of "responder analysis" will be undertaken to estimate the odds of at least a 30% reduction, relative to Visit 1, in the pain index at Visit 4. Likewise, another threshold of responder analysis will describe the odds of experiencing at least a 50% reduction. These estimates will be calculated from a logistic model in which the dependent variable is a binary variable that dichotomizes the change score at the appropriate threshold (i.e.,  $\geq 30\%$  or  $\geq 50\%$ ).

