8.3 Analysis Methods

The ITT population will be used in all analyses unless otherwise stated. The alpha level for determining significance will be set to 0.05 for all inference tests. The mixed models analyses described below automatically adjust for missing values; there will be no further imputation or adjustments for missing values. During the analysis of the primary hypothesis, treatment allocation will be masked (i.e., groups will be labeled A and B) during the statistical programming and unmasked only after the statistical programming code has been finalized.

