8.3.1 Primary Efficacy Analyses

The primary statistical analysis to evaluate the primary hypothesis will use all data from the ITT analytical sample in a linear mixed model. Mixed models will be used to analyze the treatment effect at V4 (Proc Mixed, SAS, version 9.4 or greater, SAS Institute, Inc., Cary, North Carolina). The mixed model will include the net change in the mean pain index as the dependent variable. The model's independent variables will include fixed effects for site, sex, race-ethnicity, the

Version 3.0 Page 14 of 25

mean pain index at V1 (as a baseline covariate), visit (V2, V3 and V4), treatment allocation (active versus placebo), and a visit by treatment interaction. Participants will be included as a random effect in the mixed model. The mixed model will be run twice assuming either a compound symmetry or an unstructured variance structure. The mixed model achieving the lowest Akaike information criterion will be selected as the best model and used for reporting of results. The model's denominator degrees of freedom will be adjusted for any possible effects of sample imbalances due to any missing values using Kenward Roger's method in SAS. For descriptive purposes (and regardless of the P-value for efficacy at Visit 4), efficacy estimates at each visit (2, 3 and 4) will be described in terms of adjusted means and 95% confidence intervals.

If there is a treatment effect, then "responder analyses" will be performed to compare the responder status of the treatment allocation groups. Participants will have their binomial responder status classified at both the 30% and 50% response threshold levels. The odds ratios of treatment group allocation on the responder status of participants at both the 30% and 50% threshold levels will be estimated using logistic regression with covariate adjustments for site and V1 weekly mean pain index. The odds ratio for the effect of treatment allocation on responder status for both the 30% and 50% threshold levels will be reported with their 95% confidence limits and their associated P-values.

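### The primary Visit 4 test takes its standard error from an AIC choice between compound symmetry and unstructured; fixing unstructured in advance holds the 5% level at almost no cost, and the extra participant random effect should be dropped.

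*SAP*

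**What the plan says.** The primary decision is a single test. Protocol 11.4.1: "The null hypothesis of no treatment effect will be rejected if the P-value at Visit 4 is" at or below 0.05. SAP 8.3 sets the level: "The alpha level for determining significance will be set to 0.05 for all inference tests".

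For the covariance, SAP 8.3.1 says "The mixed model will be run twice assuming either a compound symmetry or an unstructured variance structure", and then "The mixed model achieving the lowest Akaike information criterion will be selected as the best model and used for reporting of results". Degrees of freedom are adjusted "using Kenward Roger's method in SAS". The same paragraph also says "Participants will be included as a random effect in the mixed model".

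Protocol 11.4.1 has only the last of these elements: "The study participant will be modeled as a random factor". It names neither candidate structure and no covariance selection by AIC, although Protocol 11.3.1 describes the method as a repeated-measures mixed model. SAP section 11 declares no change from the protocol. SAP 8.3.2 repeats the two-structure AIC choice for the COMT haplotype model and carries the primary model over to the continuous and count secondary measures.

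**The concern.** Compound symmetry assumes the same residual variance at weeks 1, 5 and 9. With a visit-by-treatment term in the model and complete data, the Visit 4 estimate is essentially the Visit 4 comparison under either structure. What changes is its standard error, because compound symmetry substitutes the average of three variances for the Visit 4 variance. If the true Visit 4 variance is above that average, the standard error is too small; if it is below, too large. AIC is meant to detect this, but with a moderate difference it often does not, and the misfitting model then supplies the reported P-value and 95% interval.

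Unequal variances are plausible. The outcome is change from V1 adjusted for V1, so its residual variance depends on how strongly each visit correlates with V1. As an illustration only, take equal marginal SDs and V1 correlations of .7 at V2 and .6 at V4. The residual SD ratio V2/V4 is then √(1−.49)/√(1−.36) = .714/.800 ≈ .89. V2 also follows one titration week, while V4 follows eight maintenance weeks.

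A second, separate matter is that the participant random effect is listed in addition to the compound-symmetry or unstructured covariance.

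**Working it through.** **Inputs.** From the documents: three post-baseline visits, level 0.05, N = 200 randomised 1:1, 10% loss to follow-up, the listed fixed effects, and the AIC rule. The only SD given is 1190 for the baseline index (Protocol 11.2). SD ratios across V2/V3/V4 and between-visit correlations are therefore assumptions. The Visit 4 P-value is taken as two-sided, which the documents do not state.

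**Plan's own figure.** No type I error is reported for the AIC rule, so there is none to reproduce. The nearest operating figure is the 94% power: 540/(1190·√(2/100)) = 540/168.3 = 3.209. One-sided, Φ(3.209 − 1.645) = 0.941; two-sided, Φ(3.209 − 1.960) = 0.894. The stated 94% thus matches a one-sided 0.05. That is outside this point, but it is why sidedness is listed as an assumption.

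**Selection threshold.** For three visits compound symmetry has 2 covariance parameters and unstructured has 6, a gap of 4. AIC adds 2 per parameter, so unstructured is chosen when −2 log L falls by more than 2 × 4 = 8.

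**Approximate size if compound symmetry is always used.** Put the true Visit 4 SD at 1 and let v be the mean of the three variances. The size is about 2·[1 − Φ(1.96·√v)].
- SDs .9/.9/1: v = (.81 + .81 + 1)/3 = .873, √v = .935, size 6.7%.
- SDs .85/.9/1: v = .844, √v = .919, size 7.2%.
- SDs 1.15/1.1/1: v = 1.178, √v = 1.085, size 3.3%.

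**Simulation of the full rule.** Null data, the SAP's fixed effects, N = 200, about 10% lost by V4, REML fits of both structures, AIC choice, Satterthwaite degrees of freedom in place of Kenward-Roger, 40,000 trials per row (Monte Carlo error about 0.1 point). Correlation is .5 unless shown.

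| SD at V2/V3/V4 | Unstructured | Compound symmetry | AIC rule | AIC picks unstructured |
|---|---|---|---|---|
| equal | 5.1% | 5.1% | 5.1% | 10% |
| equal, correlations .6/.4/.6 | 5.1% | 5.2% | 5.1% | 97% |
| .95/.98/1 | 5.1% | 5.6% | 5.5% | 15% |
| .9/.9/1 | 5.1% | 6.8% | 5.8% | 40% |
| .88/.92/1, r = .3 | 5.0% | 6.8% | 5.8% | 38% |
| .85/.9/1 | 5.1% | 7.3% | 5.7% | 64% |
| .8/.9/1 | 5.1% | 7.9% | 5.3% | 88% |
| .7/.85/1 | 5.1% | 9.5% | 5.1% | 99.9% |
| 1.15/1.1/1 (falling) | 5.1% | 3.5% | 4.6% | 51% |

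The compound-symmetry column agrees closely with the formula. A simpler simulation with 180 completers and 100,000 trials per setting gave 5.2% to 5.9% under the AIC rule for moderately rising SDs, 4.5% to 4.9% for falling SDs, and about 5.0% for unstructured fixed in advance.

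**Participant random effect.** A random intercept adds one constant to every variance and covariance. Added to compound symmetry it is still compound symmetry, now with 3 parameters for 2 quantities. Added to unstructured it is still unstructured, with 7 for 6. Neither is identified, but a converged fit gives the same Visit 4 estimate and standard error, and the AIC gap is still 7 − 3 = 4. If software counted the extra parameter in only one model, the cut-off would move to 6 or 10. With SDs .9/.9/1 the size would then be 5.4% or 6.0%, against 5.8% at 8.

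**The case against.** The best defence is that the SAP already controls this. Both structures, the criterion and the degrees-of-freedom method are fixed in advance, and SAP 8.3 keeps the arms masked until the code is final. AIC does not look at the treatment P-value. When variances differ a lot it almost always picks unstructured, and when they do not differ either structure is valid. What is left is a middle band where the error is under one point, in a Phase II trial. All of that stands and limits the weight of the point. It does not give a reason to keep compound symmetry as a candidate, because unstructured held its level in every setting tried, including equal variances.

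It can also be said that the random-effect sentence is loose wording for within-participant covariance, given how Protocol 11.3.1 describes the model. That is a fair reading, and it makes the repair one of wording.

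Two stronger readings are tempting and should be resisted. A reader might infer that the redundant random effect itself inflates the test; the parameter count above shows that a converged fit and the AIC gap are unchanged. A reader might also quote the rejection rate among trials where compound symmetry was kept, for example 6.8% with SDs .9/.9/1, as the type I error. It is a conditional rate. In the same setting the trials that chose unstructured rejected in about (5.82 − .597 × 6.81)/.403 ≈ 4.4%, and the overall rate is 5.8%.

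**Conclusion.** The point holds as a modest specification weakness. Under the AIC rule the two-sided Visit 4 size is about 5.2% to 5.9% if the SD rises moderately by Visit 4, about 4.5% to 4.9% if it falls, and nominal if variances are equal or strongly different. Unstructured fixed in advance gives about 5.0%. These figures rest on assumed SD patterns and correlations, a two-sided test and roughly 10% loss.

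A reader might conclude that the plan is anti-conservative or has materially lost control of alpha. The documents do not support that: they give no SD of change by visit, so the direction is unknown, and the departure is below one percentage point in either direction. No size was calculated for the COMT interaction contrast; there the point is only that the same rule is reused.

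The random effect is a separate drafting fault. Its practical risk is non-convergence with no stated fallback. If unstructured failed and compound symmetry were used by default, the size would be 6.8% to 9.5% for the rising-SD rows from .9/.9/1 to .7/.85/1.

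**What to change.** In SAP 8.3.1:
- Prespecify one model: unstructured covariance over V2, V3 and V4 within participant (a REPEATED specification) with Kenward-Roger degrees of freedom.
- Delete the separate participant random effect and the AIC step for the covariance.
- Name a heterogeneous-variance structure as the fallback, to be used only if the unstructured fit does not converge.

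In SAP 8.3.2, use the same structure for the COMT model. The AIC comparison of continuous with categorical haplotype coding is a separate matter and is not addressed here.

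In SAP section 11, list the covariance specification as a change from Protocol 11.4.1.

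The cost is SAP wording and four more covariance parameters than compound symmetry (6 against 2), which is negligible with three visits and about 200 participants. No data collection changes.

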8.3.2 Secondary Efficacy Analyses

For secondary efficacy measures that are continuous variables or counts (Table 8-1), the effect of treatment arm on the net change in the secondary efficacy measures will be analyzed using the same statistical model as in the primary efficacy analyses but with derived scores for each measure used as the dependent variables. In summary, data from all applicable visits will be analyzed with linear mixed models as described for the primary hypothesis. For most secondary efficacy measures, the data were collected at V1, V3 and V4, although the schedule differed for a few data forms as shown in Appendix A. Outcomes will be reported at each study visit using number of subjects, the mean \pm standard error, and 95% confidence limits of the mean, median, min, and max. Tests for significance of treatment group differences in the change from V1 to V4 will be evaluated with linear mixed models as described for the primary hypothesis. P-value testing for the main effects of treatment allocation will be reported for overall treatment effect and for the treatment effects at each study visit.

For secondary efficacy variables measured on an ordinal scale, the non-parametric signed-rank Wilcoxon test will instead be used to test for change between visits within each treatment group,

Version 3.0 Page 15 of 25

and there will be no adjustment for covariates. Patients' Global Impression of Change is the one secondary-efficacy measure that was not measured at V0 or V1, so the test for treatment group differences in that outcome will be evaluated using the Wilcoxon rank sum.

To test the secondary hypothesis of gene-by-treatment interaction, the linear mixed model described for the primary analysis will be extended by adding three sets of predictor variables: (1) the number of COMT LPS haplotypes (0, 1, or 2) will be modeled as a fixed effect (both as a continuous variable and as a categorical variable); (2) two-way interactions between haplotype effect and treatment allocation and between haplotype effect and visit sequence; and (3) a threeway interaction term between the haplotype effect, treatment allocation, and visit sequence. The gene-by-treatment interaction at V4 is the interaction of interest. A contrast statement within the mixed model will test for a gene-by-treatment interaction at V4 with a P-value ≤ 0.05 considered statistically significant. Both an unstructured and compound symmetry variance structure, as well as, fitting the haplotype variable as a continuous (linear) and a categorical variable will be tested. The statistical model with the lowest Akaike information criterion will consider the best model and used for inference testing. Residual analysis will be used to confirm that there are no major violations of model assumptions. Model adjusted means will be reported with their 95% confidence intervals. For descriptive purposes, a second set of secondary analyses will be performed on the valine allele of the *COMT* gene using valine allele (Val/Met allele) counts in an identical manner as for the LPS haplotype counts described. A third set of secondary analyses will adapt the approach for analysis of the LPS haplotype, restricting the model to non-Hispanic whites. This is consistent with the approach of some genetic researchers who advocate racialgroup restriction as a preferable analytic method to control for population stratification.

The participants' use of rescue medications for TMD pain as well as over-the-counter analysis as well as over-the-counter analysis as well as over-the-counter analysis. (namely, NSAIDs, acetaminophen, and aspirin) for the treatment of any type of pain during a period from V1 to V4 will be summarized by treatment group, both overall and by study visit. The number of days on over-the counter analgesics and the number of days on over-the counter analgesics as a ratio of days on study drug will be summarized (n, mean and standard error) by treatment group, both overall and by study visit. Log-transformed linear regression models will test for treatment group effects on the total number of days a participant is on rescue medications for the treatment of TMD-related pain and (in a separate analysis) for over-the-counter analgesics for the treatment of any pain. The days on rescue medications (or over-the-counter analgesics for any pain) will be log-transformed and used as the dependent variable. If there are some participants with 0 days on rescue medications (or over-the-counter analgesics), then a log(x+1) transformation of days will be used to prevent log(0) values. Study site, mean pain index at V1, and days on study (log-scale) will be used as covariates in the statistical models. Adjusted mean estimates and their 95% confidence intervals of the model adjusted days on rescue medications (or analgesics for any pain) will be reported with their treatment group effect p-values. If residual analysis suggests that model assumptions are unreasonable, then the following alternative model will be used to test for treatment group effects on the use of rescue medications (or over-the-counter analgesics for any pain). This alternative model will be a generalized linear mixed model using a negative binomial link with days on rescue medications (or over-the-counter analgesics for any pain) as the dependent variable and covariates for study site, mean pain index at V1, and for days on study.

Version 3.0 Page 16 of 25

There are approximately 20 participants that were enrolled early at UB who did not have the "type of pain" documented when taking over-the-counter analgesics. It cannot be known whether the over-the-counter analgesics were taken due to TMD pain (i.e., rescue medications) and thus these 20 participants will be excluded from the above treatment group effects on the rescue medication use analysis. These subjects will be included in the use of over-the-counter analgesics for any pain.

All of the above secondary efficacy analyses are secondary to and supportive of the primary hypothesis analysis, and thus no statistical corrections will be made for multiplicity for any of the secondary analyses. P-values ≤ 0.05 will be considered statistically significant.

Additional secondary analyses of the incidence of adverse events are described in Section 9.

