## **6.2 Screening and Baseline Visit 0 (Day -21 to Day-7)**

The following procedures and assessments will be conducted up until the time of screen failure:

- 1) Obtain consent for study participation
- 2) Obtain consent to store biological specimens for future studies
- 3) Obtain signed Health Insurance Portability and Accountability statement (as applicable)
- 4) Collect demographic information
- 5) Obtain medical history
- 6) Administer the AUDIT Questionnaire
- 7) Administer the Smoking Questionnaire
- 8) Administer the Symptom Inventory
- 9) Record concomitant medications
- 10) Record specified concomitant therapies
- 11) Collect physical measurements
- 12) Collect vital signs
- 13) Perform a urine pregnancy test in female participants of childbearing potential
- 14) Administer the Fibromyalgia Questionnaire
- 15) Perform the manual tender point examination
- 16) Administer the SF-McGill Pain Questionnaire
- 17) Perform TMD examination
- 18) Review eligibility criteria
- 19) Perform pressure and heat pain tests (baseline data)
- 20) Dispense outcome measure questionnaires as shown in Schedule of Events
- 21) Dispense new Daily Symptom Diaries
- 22) Schedule next visit

---

23) Perform a screening ECG

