12.2 Schedule of Events

Study Phase:	Pre-screening ^a	Screening and Baseline	Randomization and Treatment (1 week titration, 8 weeks maintenance, and 1 week taper)				Follow-Up
Clinic Visit:		V0	V1 ^b	V2	V3	V4	V5
Study Day:	≤ 28 days prior to V0	7 to 21 days prior to V1	0	7 (+ 3)	35 (± 7)	63 (+ 6)	77 (+ 7)
Procedure							
Contact Information	X						
Prescreening Interview Script	X						
Informed Consent ^c		X					
Eligibility Review	X	x	X				
AUDIT Questionnaire		X					
Smoking Questionnaire		X					X
Alcohol Consumption per week			X	x	X	X	X
Demographic Information		x					
Medical History and Review	X	X	X	X	X	X	X
Concomitant Medications		x	X	X	X	X	X
Concomitant Therapies		x	X	x	X	X	X
Dispense New Daily Symptom Diaries		x	X	X	X	X	
Adverse Event Review			X	X	X	X	X
Collect Daily Symptom Diaries			X	X	X	X	X
Assess Compliance with Daily Symptom Diaries			X	X	X	X	X
Collect Confidence in Treatment Outcome			X				
Randomization			X				
Dispense Study Drug			$\mathbf{x}^{\mathbf{d}}$	X	х	x	
Collect Study Drug Container(s)				X	X	X	X
Assess Compliance with Study Drug				X	X	X	X
Clinical Examinations and Tests							
Physical Measurements		X					

Study Phase	: Pre-screening ^a	Screening and Baseline	Randomization and Treatment (1 week titration, 8 weeks maintenance, and 1 week taper)				Follow-Up
Clinic Visit	:	V0	V1 ^b	V2	V3	V4	V5
Study Day	$ \begin{array}{ c c c c c c c c c c c c c c c c c c c$	7 to 21 days prior to V1	0	7 (+ 3)	35 (± 7)	63 (+ 6)	77 (+ 7)
Vital Signs		X	X	X	X	X	X
Urine Pregnancy Test (females)		x	X	X	X	X	x
Manual Tender Point Exam		X					
TMD Examination		X			X	X	
Heat and Pressure Pain Tests		x			X	X	
12-Lead ECG		x					
Blood Draw			X			X	
Schedule Next Visit	X	x	X	х	X	X	
Outcome Measure Questionnaires							
Symptom Inventory		X	X	X	X	X	X
Fibromyalgia Questionnaire		x					
Headache Questionnaire ^e			X				
SF-McGill Pain Questionnaire		X		Х	X	X	х
Graded Chronic Pain Scale ^e			X		X	X	
SF-12 Health Survey v2 ^e			X		X	X	
Jaw Functional Limitation Scale ^e			Х		Х	Х	
Perceived Stress Scale ^e			X		X	X	
Hospital Anxiety and Depression Scale ^e			Х		х	х	
Pittsburgh Sleep Quality Index ^e			х		х	х	
Headache Impact Test (HIT-6) e			X		X	X	
SCL-90R Somatization Scale ^e			Х		х	х	
Coping Strategies Questionnaire-Revised ^e			X				
Patient Global Impression of Change ^e					Х	Х	

AUDIT = Alcohol Use Disorders Identification Test; ECG = electrocardiogram; SCL-90 = Symptom Checklist -90R; SF = Short Form; V = Visit

Version 3.0 Page 24 of 25

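### The planned change from V1 to V4 cannot be computed for 19 of the 38 mixed-model secondary variables, and the reused model, read literally, adjusts for the V1 pain index instead of each outcome's own baseline

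*SAP*

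**What the plan says.** SAP 8.3.2 analyses continuous and count secondary outcomes "using the same statistical model as in the primary efficacy analyses but with derived scores for each measure used as the dependent variables". It then fixes the contrast: "Tests for significance of treatment group differences in the change from V1 to V4 will be evaluated with linear mixed models as described". The model being reused is in SAP 8.3.1, whose independent variables include "mean pain index at V1 (as a baseline covariate), visit (V2, V3 and V4" and treatment by visit.

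SAP 8.3.2 adds that most secondary measures were taken at V1, V3 and V4, and that some forms followed a different schedule. It names no other baseline visit for those forms. Table 8-1 writes out a subtraction of the V1 value only for the diary measures; the other rows define a score per visit.

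In the schedule (Protocol Appendix A, SAP 12.2), the rows for "Heat and Pressure Pain Tests" and for the TMD examination are marked at V0, V3 and V4. The SF-McGill is marked at V0, V2, V3, V4 and V5. None is marked at V1, and none appears in the Visit 1 list of Protocol 6.3.1. The Visit 0 list in Protocol 6.2 has the entry "Perform pressure and heat pain tests (baseline data").

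**The concern.** A change from V1 needs a V1 value. The assessments without one make up the whole experimental-pain domain, which is a named secondary objective, and much of the clinical-pain domain. Followed to the letter, the rule gives no result for them. Followed sensibly, the analyst substitutes a baseline that the plan does not name.

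The covariate is a second, softer problem. If only the dependent variable is swapped, each outcome's change is adjusted for the pain index and not for that outcome's own pre-treatment value, although the trial collects that value. Secondary P-values are judged at 0.05 without multiplicity correction (SAP 8.3.2), and Protocol 11.4.1 unmasks allocation after the primary analysis. The choice of covariate should therefore be settled in the plan.

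**Working it through.** The documents give no count of secondary variables, so there is no stated figure to reproduce.

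**Step 1. Count the variables.** Each secondary row of SAP Table 8-1 is matched to the schedule of events.

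| Measure | Variables | Pre-dose value at | Planned test |
|---|---|---|---|
| Diary intensity, diary duration | 2 | V1 | mixed model |
| Heat threshold, heat tolerance | 2 | V0 only | mixed model |
| Pressure pain threshold, five sites | 5 | V0 only | mixed model |
| SF-McGill, two subscales and four items | 6 | V0 only | mixed model |
| TMD examination, jaw opening | 3 | V0 only | mixed model |
| TMD examination, counts of painful locations | 3 | V0 only | mixed model |
| Vital signs | 3 | V0 and V1 | mixed model |
| SF-12 | 2 | V1 | mixed model |
| HIT-6 | 1 | V1 | mixed model |
| GCPS intensity, interference | 2 | V1 | mixed model |
| GCPS grade (ordinal) | 1 | V1 | signed-rank |
| HADS | 2 | V1 | mixed model |
| PGIC at V3 and V4 (ordinal) | 2 | none | rank sum |
| JFLS | 4 | V1 | mixed model |
| PSS, SCL-90R, PSQI | 3 | V1 | mixed model |

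- All secondary variables: 41.
- Assigned to the mixed model: 41 − 2 (PGIC) − 1 (GCPS grade) = 38.
- Mixed-model variables without V1: 2 + 5 + 6 + 3 + 3 = 19, which is 19/38 = 50%.
- Of those 19, measured at V0: 19.
- Any secondary variable without V1: 19 + 2 (PGIC) = 21 of 41.
- Exactly on the V1, V3, V4 pattern: 2 + 1 + 2 + 1 + 2 + 4 + 3 = 15 of 41. The SAP's remark that most measures follow it is not true by variable.

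The SAP does not give the scale of the four SF-McGill items; they are counted here as continuous.

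**Step 2. Bias.** Randomisation gives both arms the same expected baseline. Expected regression to the mean is then equal in the two arms and cancels in their difference. The covariate choice affects precision and the handling of chance imbalance, not bias.

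**Step 3. Precision, upper illustration.** Let baseline and follow-up have equal variance s² and correlation r, with the pain index uninformative.

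- Variance of change: 2s²(1 − r).
- Residual variance adjusting for own baseline: s²(1 − r²).
- Ratio: (1 − r²) / [2(1 − r)] = (1 + r)/2.

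The documents give no r. For assumed r = 0.4, 0.5, 0.6 and 0.8 the ratio is 0.70, 0.75, 0.80 and 0.90.

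**Step 4. Precision when the pain index is close to the outcome.** Assume the index correlates 0.9 with the outcome's own baseline and relates to follow-up only through it. Adjusting the change for the index leaves s²[2(1 − r) − 0.81(1 − r)²]. The ratio becomes (1 + r) / [2 − 0.81(1 − r)].

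- r = 0.4: 1.4/1.514 = 0.92
- r = 0.5: 1.5/1.595 = 0.94
- r = 0.6: 1.6/1.676 = 0.95
- r = 0.8: 1.8/1.838 = 0.98

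The gain falls to about 2% to 8%. Diary intensity and duration are the likely cases, because the daily pain index is their product (Protocol 2.5.1).

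**The case against.** V0 is the obvious substitute. The SAP acknowledges that some forms follow another schedule, and that schedule shows V0. It singles out PGIC as the only measure with neither a V0 nor a V1 value, which implies that either visit can serve as baseline for the rest. Protocol 6.2 labels the V0 pressure and heat tests as baseline data. Each affected form has one scheduled pre-dose assessment, so there is little room to choose. A reader might infer that half of these outcomes will end up without a valid analysis; the documents do not support that. What stands is that the written contrast names V1, and no sentence replaces it. Nor is V1 simply the SAP's word for baseline: SAP 8.3.3 assigns smoking and tender points to V0 and catastrophizing to V1.

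On the covariate, the same model can fairly be read as the same structure with each outcome's own baseline put in. Protocol 11.4.1 is worded generally: "The baseline score collected at Visit 1 will be the continuous covariate, modeled as a fixed effect". That may be what was meant. However, the sentence describes the primary model, the SAP names the pain index specifically, and its instruction for secondary outcomes swaps only the dependent variable. SAP 8.3.2 also uses the V1 pain index as covariate for days on rescue medication, but no pre-treatment value of that outcome is specified there, so this does not settle the intent.

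Finally, the SAP calls these analyses supportive of the primary one. That limits the consequence but does not remove the mismatch.

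**Conclusion.** The concern holds in two parts of unequal strength. The firm part is that the contrast as stated cannot be computed for 19 of the 38 mixed-model secondary variables. This rests only on Table 8-1 and the schedule. The conditional part is that, on a literal reading, the wrong baseline covariate is carried over. Its cost is lost precision and unadjusted chance imbalance in the outcome's own baseline.

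Two stronger conclusions are tempting and should not be drawn. One is that regression to the mean biases the secondary comparisons; randomisation rules that out for the between-arm contrast. The other is that own-baseline adjustment would save 10% to 30% of the variance throughout. That range depends on assumed correlations of 0.4 to 0.8, equal variances and an uninformative pain index. It is an upper illustration, with only a few percent to gain where the outcome tracks the index closely.

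The primary analysis is unaffected: its endpoint has a V1 value, which is its covariate. The SAP should be corrected, but the main conclusion of the trial does not depend on it.

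**What to change.** Add to SAP 8.3.2 a definition of baseline for each continuous or count secondary variable as its last pre-dose value: V0 for heat tests, pressure thresholds, the TMD examination and the SF-McGill, and V1 for all others. Taking the last pre-dose value also covers a repeated Visit 0, which the schedule's footnote allows. Then state that change is measured from that baseline, that the treatment difference in change to V4 is the tested contrast, and that this baseline replaces the V1 mean pain index as the continuous covariate.

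The cost is about two sentences in the SAP and the matching programming. Every value needed is already scheduled. Protocol 11.4.2 leaves these details to the SAP, so its text need not change.
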